6.3 Exposure During Pregnancy and/or Lactation

OV101 should not be administered to pregnant or lactating females because the potential for adverse reactions to OV101 in pregnant females, fetuses, and nursing infants is unknown.

Pregnancy data will be collected during this study for all study participants. Exposure during pregnancy (also referred to as exposure in-utero) can be the result of either maternal exposure or transmission of drug product via semen following paternal exposure.

Exposure during pregnancy must be recorded and the study participant followed until the outcome of the pregnancy is known (spontaneous miscarriage, elective termination, normal birth, or congenital abnormality), even if the study participant discontinues study drug or discontinues from the study.

If a study participant within this study or a study participant's partner becomes pregnant while treated or exposed to study drug, the investigator must submit a pregnancy form to Ovid via the same method as SAE reporting (Section 6.2.1.5). Pharmacovigilance will supply the investigator with a copy of a "Pregnancy Reporting and Outcome Form/Breastfeeding." When the outcome of the pregnancy becomes known, the form should be completed and returned to Ovid or Ovid Pharmacovigilance delegate. If additional follow-up is required, the investigator will be requested to provide the information.

Exposure of an infant to an Ovid product during breastfeeding must also be reported and any AEs experienced by the infant must be reported to Ovid Pharmacovigilance or designee via email (Section 6.2.1.5).

Pregnancy is an outcome of an event and should not be reported as an AE unless there is a suspicion that study drug may have interfered with the effectiveness of a contraceptive medication. However, complications of pregnancy and abnormal outcomes of pregnancy are AEs and may meet criteria for an SAE (such as ectopic pregnancy, spontaneous abortion, intrauterine fetal demise, neonatal death, or congenital anomaly). Elective abortions without complications should not be reported as AEs

6.4 Pregnancy

Female study participants who are of childbearing potential (defined as having experienced their first menarche) must agree to use either a highly effective or acceptable form of birth control during the study and for 30 days following the last dose of the study drug. Highly effective contraceptive methods are as follows:

- a. Combined (estrogen- and progestogen-containing) hormonal contraception associated with inhibition of ovulation:
 - Oral
 - Intravaginal
 - Transdermal

- b. Progestogen-only hormonal contraception associated with inhibition of ovulation:
 - Oral
 - Injectable
 - Implantable
- c. Intrauterine device
- d. Intrauterine hormone-releasing system
- e. Bilateral tubal occlusion
- f. Vasectomized partner
- g. Sexual abstinence

Acceptable birth control methods that result in a failure rate of more than 1% per year include:

- a. Progestogen-only oral hormonal contraception, where inhibition of ovulation is not the primary mode of action.
- b. Male or female condom with or without spermicide.
- c. Cap, diaphragm, or sponge with spermicide.
- d. A combination of male condom with either cap, diaphragm, or sponge with spermicide (double barrier methods) are also considered acceptable, but not highly effective, birth control methods.

For male study participants with women of childbearing potential partners, there are no restrictions. Female study participants who have experienced menarche and are not surgically sterile will undergo serum (or urine) beta-human chorionic gonadotrophin (β -hCG) pregnancy testing at clinic visits shown in Table 6-1. After the screening and baseline visits, if serum is not obtainable, urine pregnancy testing is allowed. Any study participant with a positive pregnancy test result at Screening or Baseline must be excluded from the study. A serum β -hCG pregnancy test must be performed if any female study participant is suspected of becoming pregnant during the study.

If pregnancy occurs at any time during the study, study drug must be discontinued immediately (or not started). Pregnancy is not regarded as an AE unless there is a suspicion that a study drug may have interfered with the effectiveness of a contraceptive medication. Any pregnancy that occurs during study participation must be reported using the same procedures as an SAE (Section 6.2.1.5) but using a clinical study pregnancy form. The pregnancy must be followed-up to determine outcome (including spontaneous miscarriage, elective termination, normal birth, or congenital abnormality) and status of mother and child, even if the study participant is discontinued from the study. Pregnancy complications and elective terminations for medical reasons should not be reported as an AE or SAE. Spontaneous miscarriages must be reported as an SAE.

Any SAE occurring in association with a pregnancy, brought to the investigator's attention after the study participant has completed the study and considered by the investigator as possibly related to the study treatment, must be promptly reported to Ovid Drug Safety.

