6.2.1.2 Serious Adverse Events

An SAE is defined as any event that:

- Results in death
- Is immediately life threatening
- Requires inpatient hospitalization or prolongation of existing hospitalization

- Results in persistent or significant disability/incapacity
- Is a congenital anomaly or birth defect

Important medical events that may not result in death, be life threatening, or require hospitalization may be considered SAEs when, based upon appropriate medical judgment, they may jeopardize the study participant or may require medical or surgical intervention to prevent one of the outcomes listed in this definition. Examples of such medical events include allergic bronchospasm requiring intensive treatment in an emergency room or at home, blood dyscrasias or convulsions that do not result in inpatient hospitalization, or the development of drug dependency or drug abuse.

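### Section 6.4 bars reporting pregnancy complications as AEs or SAEs, while Section 6.3 classes them as AEs and possible SAEs, so a qualifying event can be missing from the AE/SAE tables

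*Combined protocol and SAP*

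**What the plan says.** Section 6.3 covers exposure during pregnancy. It states that "complications of pregnancy and abnormal outcomes of pregnancy are AEs and may meet criteria for an SAE", and its examples include ectopic pregnancy, intrauterine fetal demise and neonatal death. On terminations it says that "Elective abortions without complications should not be reported as AEs".

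Section 6.4 covers pregnancy more generally. It states that "Pregnancy complications and elective terminations for medical reasons should not be reported as an AE or SAE", followed at once by one exception: "Spontaneous miscarriages must be reported as an SAE". Any pregnancy during participation "must be reported using the same procedures as an SAE (Section 6.2.1.5) but using a clinical study pregnancy form", and is followed to outcome. A closing paragraph requires prompt reporting of a pregnancy-associated SAE that is "brought to the investigator's attention after the study participant has completed the study and considered by the investigator as possibly related to the study treatment".

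The general rules make no exception for pregnancy. Section 6.2.1.1 makes the investigator responsible for reporting all AEs, whatever their severity or relationship to study drug. The SAE criteria in 6.2.1.2 include immediately life-threatening events and any event that "Requires inpatient hospitalization or prolongation of existing hospitalization". Section 6.2.1.5 requires an event meeting those criteria to be reported to the sponsor and entered in the EDC system within 1 business day.

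The primary objective (2.1) is the incidence and severity of AEs and SAEs. Sections 7.1 and 7.7.1 tabulate SAEs and TEAEs. Neither names a table of pregnancy-form data.

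**The concern.** The two adjacent sections give opposite instructions on the same class of event, and a site cannot obey both. Whether a complication of pregnancy enters the AE/SAE record then depends on which section the site consults.

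Two things are at stake. The first is the count: the safety tables are built from AE and SAE records, so an event held only on a pregnancy form has no planned place in them. The second is timing: the 1-business-day SAE record attaches to an event recorded as an SAE. Section 6.3 asks for the pregnancy outcome form once the outcome is known and sets no deadline for it. A complication that arises after the first pregnancy notice could therefore reach the sponsor later than an SAE would.

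The situation is foreseeable. Post-menarchal females are eligible (inclusion criterion 9), treatment lasts 160 weeks, and 6.3 itself says that the potential for harm in pregnancy is unknown.

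**Working it through.** The plan states no figure on this point, so the check is a comparison of the texts, followed by an illustration of size.

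**Step 1. The rules side by side.**

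| Event | Section 6.3 | Section 6.4 | Consistent? |
|---|---|---|---|
| Pregnancy itself | Not an AE unless contraceptive interference is suspected | Same | Yes |
| Pregnancy complication (e.g. ectopic pregnancy) | AE, possibly SAE | Not to be reported as either | **No** |
| Elective termination for medical reasons, with a complication | The complication is an AE | Not to be reported as either | **No** |
| Elective termination for medical reasons, no complication | Not an AE | Not an AE or SAE | Yes |
| Elective termination for other reasons, no complication | Not an AE | Not addressed by the sentence | Gap only |
| Spontaneous miscarriage | May meet SAE criteria | Always an SAE | Yes: following 6.4 satisfies both |

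The direct conflict is therefore limited to complications, including those of medically indicated terminations.

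**Step 2. Section 6.4 against the general definitions.** Take an ectopic pregnancy that leads to inpatient admission. Under 6.2.1.1 it is an untoward medical occurrence in a participant, hence an AE. Under 6.2.1.2 admission makes it serious. Under 6.2.1.5 it is reportable within 1 business day. Section 6.4 says it should not be reported as either. The closing paragraph of 6.4 also assumes that a pregnancy can have an associated SAE, but it covers only possibly related events learned of after study completion. It does not cure the in-study conflict.

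**Step 3. What a site following 6.4 would submit.** It would send a pregnancy form by the SAE procedure and follow the pregnancy to outcome. There would be no AE page and no SAE record for the complication, so the event would not appear in the 7.7.1 tables.

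**Step 4. Could the event fall in the TEAE window?** Drug stops when pregnancy occurs (6.4), and the window closes 30 days after the last dose (7.7.1), so many later complications would fall outside it under either section. However, Table 6-1 schedules pregnancy tests only at clinic visits. After Week 12 the gaps are 36 − 12 = 24, 64 − 36 = 28, 96 − 64 = 32, 128 − 96 = 32 and 160 − 128 = 32 weeks. Unless pregnancy is suspected sooner, dosing could continue for some weeks, and an early complication could occur on treatment.

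**Step 5. Illustration of size.** Assume n = 170 in the safety set (planned enrollment, Section 7.4) and x participants with a disputed complication. The documents give no basis for x, so 0 to 2 is only a range for illustration. The exact 95% interval (the type named in 7.7.1) has lower limit Beta(0.025; x, n − x + 1), taken as 0 when x = 0, and upper limit Beta(0.975; x + 1, n − x).

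| x | x/170 | Exact 95% CI |
|---|---|---|
| 0 | 0% | 0 to 2.15% |
| 1 | 0.59% | 0.01 to 3.23% |
| 2 | 1.18% | 0.14 to 4.19% |

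Omitting the only such case changes the row from 1/170 to 0/170. Overall TEAE incidence can move by at most 0.59 percentage points, and does not move at all if that participant has any other TEAE.

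**The case against.** The strongest reply is that the sponsor still learns of every pregnancy. Both sections send it by the SAE method, follow it to outcome, and do so even if the participant leaves the study. Section 6.2.1.1 says that fetal-outcome data are collected for regulatory reporting and drug safety evaluation. This stands. A reader might infer that 6.4 hides these events from the sponsor or removes them from all expedited handling, and the documents do not support that. What is lost is the classification as an AE or SAE, the tabulation, and the SAE clock for the complication itself.

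A second reply is that 6.2.1.8 tells sites to report when in doubt whether an observation is an AE. This softens the conflict without resolving it, because 6.4 is an explicit instruction and leaves nothing in doubt.

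A third reply is that the effect on the tables is slight: drug is stopped, the TEAE window is short, and events in partners or infants would not enter participant incidence. This largely stands and limits the size of the point. It does not remove the point, because an early complication can precede detection of the pregnancy, and 7.1 lists SAE incidence separately from TEAEs.

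Two further inferences should be resisted. The miscarriage wording is not a contradiction, since always an SAE is compatible with may be an SAE. Nor does 6.4 bar reporting a congenital anomaly: it lists congenital abnormality as an outcome to be followed up, and its prohibition does not name it. The 6.2.1.2 criterion "Is a congenital anomaly or birth defect" is therefore not where the clash lies. The relevant criteria are life-threatening events and hospitalization.

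**Conclusion.** The contradiction is definite and lies in current text. Section 6.4 forbids recording as an AE or SAE a class of event that 6.3 calls an AE and that can meet the 6.2.1.2 criteria for seriousness. A site following 6.4 as written would leave a qualifying complication out of the tables serving the primary objective and outside the 1-business-day SAE record.

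The expected number of events is low and cannot be estimated from the documents. A reader might take a proportion such as 2/170 as the size of the problem. The documents do not support that: the numerator is assumed, the denominator includes males and pre-menarchal children, and a count of pregnancies is not a count of complications. What can be said is that a single omitted case decides whether a preferred-term row appears at all, while overall incidence barely changes.

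The conclusion rests on two assumptions: that sites apply 6.4 literally, and that the safety tables draw on AE and SAE records and not on pregnancy forms. Sections 7.1 and 7.7.1 support the second.

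**What to change.** Reconcile the 6.4 sentence with 6.3 so that both sections state one reporting rule for pregnancy complications and for elective terminations, consistent with the AE and SAE definitions in 6.2.1.1 and 6.2.1.2. Use the same description of elective terminations in both places, since exclusion for lack of complications and exclusion for medical reasons cover different sets. State that the pregnancy form is an additional report and does not replace the AE or SAE record.

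The cost is a few sentences in 6.3 and 6.4, plus a note to sites. Visits, treatment and sample size are unaffected. Section 7.7.1 can stay as it is, because it tabulates whatever is recorded as an AE or SAE.

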6.5 Contraception and Pregnancy Avoidance Procedures

Please refer to Section 6.4 for detailed contraception requirements.

Study participants will be provided with information on acceptable methods of contraception as part of the study participant informed consent process and will be asked to sign a consent form stating that they understand the requirements for avoidance of pregnancy during the study and for 30 days after the last dose of study drug and avoidance of donation of ova or sperm during the course of the study and for 90 days after the last dose of study drug. This may be signed by the LAR/caregiver of the study participant.

Female study participants who have experienced menarche must have a negative serum β -hCG pregnancy test at Screening (Visit 1) and a negative serum β -hCG pregnancy test on Day 1 (Visit 2), before receiving any dose of study drug. If pregnancy results cannot be collected at Visit 2, the reason should be documented in the source document, the results of the serum pregnancy test obtained at Visit 1 must be confirmed to be negative by the investigator prior to randomization, and results of a serum pregnancy test at Visit 2 must be confirmed to be negative before the study participant can receive the first dose of study drug. During the study, study participants will receive continued guidance with respect to the avoidance of pregnancy and ova or sperm donation as part of the study procedures. An additional serum β -hCG pregnancy test will be performed at the EOT visit.

6.6 Safety Monitoring Committee

The Safety Monitoring Committee is described in Section 11.1.1.

6.7 Laboratory Analyses

The following clinical analytes will be assessed:

Hematology (safety assessment): hematocrit; hemoglobin; red blood cell count with indices (mean corpuscular volume, mean corpuscular hemoglobin, and mean corpuscular hemoglobin concentration); reticulocytes; white blood cell count and differential (neutrophils, lymphocytes, monocytes, eosinophils, and basophils) reported as percentages and absolute values; and platelets (platelet count, prothrombin time and partial thromboplastin time, international normalization ratio).

Clinical chemistry (safety assessment): albumin; alkaline phosphatase; blood urea nitrogen; gamma-glutamyl transferase; calcium; creatinine; glucose; cholesterol (high-density lipoprotein and low-density lipoprotein [calculated] and homogenous low-density lipoprotein); triglycerides; phosphate; potassium; alanine aminotransferase; aspartate aminotransferase; lactate dehydrogenase; sodium; chloride; bilirubin (total, direct); total protein; uric acid; and creatine phosphokinase.

6.7.1 Sample Collections

Blood samples collected from study participants will be forwarded to a central laboratory for analysis. Further details regarding sample collections and processing and specific testing can be found in the central laboratory manual (provided to study sites as a separate document).

All samples for clinical laboratory analysis will be collected as described in the central laboratory manual, according to the schedule of activities (Table 6-1). Samples for hematology, clinical chemistry, or urinalysis (pregnancy testing only) will be used only for the evaluation of safety and tolerability.

Blood samples will be collected only for clinical laboratory safety assessments. The maximum volume of blood to be collected per study participant over the course of the study is estimated to be less than 175 mL.

6.8 Efficacy Assessments

Efficacy assessments will be conducted according to the schedule presented in Table 6-1. The efficacy assessments, grouped by efficacy domain and participant source, are presented in Table 6-2. Every effort should be made to have the same LAR/caregiver complete the LAR/caregiver-reported assessments. Additionally, every effort should be made to have the same investigator and raters complete the clinician assessments.

Efficacy assessments are only to be conducted in study participants who are at least 4 years old at study entry. If a study participant is 2 to 3 years old at study entry and turns 4 years old during the course of the study, only safety assessments are to be continued.

Table 6-2 Efficacy Assessments by Domain and Participant Source

Domain	LAR/Caregiver Assessment	Clinician Assessment
Sleep	
• Children's Sleep Habits Questionnaire• Sleep diary	—
Motor	—	
• Vineland Adaptive Behavior Scale (Motor domain)
Global functioning and quality of life	
• Pediatric Quality of Life Inventory	
• Vineland Adaptive Behavior Scale (Socialization, Communication, Daily Living Skills, and Maladaptive Behavior domains)• CGI-AS scales

Abbreviations: CGI-AS, Clinical Global Impressions-Angelman syndrome; LAR, legally acceptable representative.

6.8.1 Caregiver Assessments

6.8.1.1 Children's Sleep Habits Questionnaire

The Children's Sleep Habits Questionnaire (CSHQ) is a retrospective, 33-item caregiver questionnaire that has been used in studies to examine sleep behavior in young children (Owens et al 2000). The CSHQ includes items relating to sleep domains that encompass the major presenting sleep complaints in this age group, evaluating the child's sleep based on sleep behaviors within 8 different subscales: bedtime resistance, sleep-onset delay, sleep duration, anxiety around sleep, behavior occurring around night waking, parasomnias, sleep-disordered breathing, and morning waking/daytime sleepiness. Caregivers will be asked to recall sleep behaviors occurring over the 7 days immediately preceding specified timepoints outlined in Table 6-1. Items are rated on a 3-point scale: "usually" if the sleep behavior occurred 5 to 7 times/week; "sometimes" for 2 to 4 times/week; and "rarely" for 0 to 1 time/week. The scoring of some items can be reversed to consistently make a higher score indicative of more disturbed sleep.

6.8.1.2 Sleep Diary

A sleep diary will be completed by each study participant's LAR/caregiver, on behalf of the study participant. Endpoints assessed by the sleep diary are presented in Section 7.2.1. The sleep diary will be completed each day during the 7 days immediately preceding each clinic visit after screening.

At each clinic visit when a sleep diary is issued (Table 6-1), a calendar will be issued to remind the LAR/caregiver when next to start recording data in the sleep diary. In addition, 14 days before the study participant's expected next visit date, study staff will phone the LAR/caregiver as a reminder to start recording data in the sleep diary.

Sleep diaries will be collected at each clinic visit, starting with the baseline visit (Table 6-1) and continuing through the EOT visit.

6.8.1.3 Pediatric Quality of Life Inventory

The Peds QL® Cerebral Palsy, Multidimensional Fatigue, and Family Impact modules will be administered in this study (Varni et al 2004; Varni et al 2005). The 22-item Cerebral Palsy module assesses daily activities, school activities, movement and balance, pain and hurt, fatigue, eating activities, and speech and communication. The 18-item Multidimensional Fatigue module assesses general fatigue, sleep/rest fatigue, and cognitive fatigue. The 36-item Family Impact module assesses the impact of pediatric chronic health conditions on caregivers and family, including caregiver-reported assessments of physical, emotional, social, and cognitive functioning, communication, and worry. It also assesses caregiver-reported family daily activities and family relationships.

For this study, the Peds QL® Cerebral Palsy, Multidimensional Fatigue, and Family Impact should be performed for all study participants, including those over the age of 25.

6.8.2 Clinician Assessments

6.8.2.1 Vineland Adaptive Behavior Scale

The Vineland Adaptive Behavior Scale, 3rd Edition (VABS-3) is a standardized psychometric instrument designed to measure personal and social skills needed for everyday living (Sparrow et al 2005; Sparrow et al 2016). The VABS-3 is administered via a caregiver using a semi-structured interview format and assesses 4 main adaptive domains: communication (receptive, expressive, and written), socialization (interpersonal relationships, play and leisure, coping skills), daily living skills (personal, domestic, community), and motor skills (fine and gross). It also includes a maladaptive behavior scale for identifying behavior problems in children through 18 years of age. The scale has been found to have good internal consistency, test-retest reliability, and validity (Sparrow et al 2016). The VABS-3 interview form will be used to evaluate study participants on the communication, socialization, daily living skills, motor skills, and maladaptive behavior domains to assess their overall functioning. This assessment is an interview of the caregiver by a trained qualified rater, and for each study site, the same rater is to

be used throughout the study. As an exception, another sponsor-trained qualified rater may be used.

